7.2.10 Exploratory endpoint: change in tumor size

Change in tumor size is defined as the difference in each tumor evaluation from the baseline measurement at the time of starting or switching to osimertinib. More information about this endpoint can be found in [Ref. 35].

7.3 Evaluation of safety

7.3.1 Adverse events

All adverse events will be recorded; the investigator will assess whether those events are related to osimertinib (reasonable possibility, no reasonable possibility) or gefitinib (reasonable possibility, no reasonable possibility) and this assessment will be recorded in the database for all adverse events.

The collection period will start from randomization and all adverse events must be followed until resolution or stabilization.

7.3.2 General evaluation of adverse events

This study will use the International Common Terminology Criteria for Adverse Events (CTCAE), version 4.0, for adverse event reporting. A copy of the CTCAE can be accessed from the EORTC home page https://www.eortc.be/services/doc/ctc/.

Hematological toxicity will be assessed on the basis of regular blood tests. The nadir count will be computed at each study medication administration and graded according to the CTCAE version 4.0.

Non hematological acute side effects will be assessed and reported separately for each study medication administration, and graded according to the CTCAE version 4.0.

Planned safety analysis and tabulations are described in the statistics section.

7.3.3 Serious adverse events

Serious adverse events are defined by the Good Clinical Practice Guideline.

Serious adverse events should be immediately reported according to the procedure detailed in this protocol (see chapter on Reporting Serious Adverse Events).

7.3.4 Toxic deaths

Toxic death is defined as death due to toxicity (defined as adverse events that are not confirmed as unrelated). The cause of death must be reported as "toxicity".

The evaluation of toxic deaths is independent of the evaluation of response (patients can die from toxicity after a complete assessment of the response to therapy).

7.3.5 Evaluability for safety

All patients who have started the treatment (either gefitinib or orsimertinib) will be included in overall safety analyses.

For hematological events, the medical review team may decide that blood counts have not been performed and/or reported according to the protocol and are therefore inadequate for the evaluation of one/several hematological parameters in some patients.

Parameters that will be identified and monitored will be the following:

- Any grade 3-4 non hematological or grade 4 hematological toxicity at least possibly related to the treatment;
- % of treatment interruptions, schedule modifications and dose modifications;
- Compliance to the requirement of minimum dose intensity of 70% (treatment tolerability rule);
- Unexpected grade 2 toxicity at least possibly related to the treatment;
- Worsening of toxicity if data will be available at the time of DSM.

Patients who have discontinued treatment because of toxicity will always be included in the safety analyses.

7.4 Evaluation of frailty using the G8 geriatric screening tool

7.4.1 Background

Older cancer patients have a much more heterogeneous general health status compared to young cancer patients. Some older patients are in perfect general health, while others are vulnerable or frail. Frailty is a well-known concept in geriatric medicine [Ref. 36]. It is defined as a multi-factorial syndrome, resulting in a reduction of the physiological reserve and of the capability to resist stressful events (homeostatic capacity). Frailty is associated with an increased risk of unfavorable clinical events: disability, hospitalization, institutionalization, death. In oncology, the construct of frailty is as well used to describe patients with increased risk of treatment-associated morbidity and mortality. Presence of frailty can be detected by a so-called (Comprehensive) Geriatric Assessment (GA). Performance of GA is advised in older cancer patients by the International Society of Geriatric Oncology, SIOG [Ref. 37]. GA is time consuming (takes about 30 minutes). Therefore, short geriatric screening tools such as the G8 have been developed as a short and easy to use measurement of general health status. The G8 score has been specifically developed in oncology, includes 8 items, takes a few minutes to complete, and can be completed by any health care worker [Ref. 38]. The score ranges from 1 to 17. A score greater than 14 indicates that there is little risk that further GA reveals significant problems in the further assessed GA domains. The G8 was shown to strongly predict functional decline and overall survival [Ref. 39]. G8 is by far the best studied geriatric screening tool in oncological patients, and also has better performance for detection of geriatric problems than other geriatric screening tools such as VES-13 [Ref. 40].

7.4.2 Assessments

G8 will be measured in all patients aged 70 years and above at baseline. G8 has to be completed by the clinician, the nurse or the trained coder. This screening tool includes 7 items of the Mini Nutritional Assessment and the age of the patient. The English version of G8 is included as a protocol appendix (Appendix D).

7.4.3 Objective

The inclusion of the G8 screening tool in EORTC trials will allow a uniform, easy and established approach of frailty at baseline. The G8 tool itself has been developed as a screening tool, and not a tool for follow-up.

The treating physician may decide which actions are needed based on the G8 result (e.g. further geriatric assessment in case of a G8 score of less or equal to 14; geriatric interventions if specific problems are detected within specific geriatric domains).

The assessment of frailty as defined by G8 in all patients aged 70 years and above entered in EORTC trials will allow interpretation of whether new treatment strategies have been tested in both fit and less fit patients which has importance for the generalizability of the study results.

8 Statistical considerations

8.1 Statistical design

8.1.1 Sample size

This study is designed with an understanding of the difficulty of having a primary endpoint which solidly covers all arms. The primary endpoint PFSR-OSI-18 as defined in Chapter 0, will be assessed in all arms, yet this endpoint will be used to evaluate arm B and arm C. With this restriction, the below criteria for a success of the arm (applicable B and C) should be viewed as exploratory and further information from secondary endpoints as well as the costs should be considered if the arm is judged as feasible to be further explored.

The study design is a 1-Stage Ahern Design - Single Proportion, with Progression Free Survival rate at 18 months (PFSR-OSI-18) as primary endpoint. It was designed with a 1-sided alpha = 0.08 and 92% power (beta = 8%).

In arm B and C of this trial, if the result is compatible with a progression free survival rate at 18 months (PFSR-OSI-18) of 60% in the studied population, the strategy should be further explored. However, if we are unable to demonstrate that the PFSR-OSI-18 in the studied population is at least 40%, the strategy should be rejected from further exploration.

49 eligible patients who started treatment are needed in each arm. To declare the arm worthwhile for further exploration, at least 25 out of 49 patients should be a success (see definition of the primary endpoint in section 7.2.1) at 18 months.

Additional 5% patients will be accrued to take into account patients who might be ineligible or not starting treatment. Hence, using a 1:1:1 ratio for randomization, a total of 156 patients will be accrued in this study (52 pts in each arm) within 26 months and an additional 24 months of follow up after the last patient entry is needed to allow the assessment of the primary endpoint. The estimated duration of the study is 6 years, given that all patients have ended their treatment according to End of Study definition (section 8.4).

In this study a minimum of 18 months of follow up is needed after the last patient entry.

8.1.2 Power to detect a difference in brain progression free survival (BPFS)

In this study, a special emphasis is given to the secondary endpoint BPFS. Formal comparison between arm A versus B and A versus C with respect to BPFS will be made. The power of such comparison is given below.

With a 1-sided alpha = 5% (so that a 1-sided family wise error: 10%, taking into account 2 comparisons), and looking for an improvement in BPFS at 18 months from 75% to 87.5% (equivalent to 54% reduction in risk of progression, i.e. HR = 0.46), 36 BPFS events will give an approximately 70% power to detect the above difference.

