8.2 Statistical analysis plan

Analyses described below will be done separately for each arm, except for the secondary endpoint BPFS where comparisons between the arms (i.e. A vs. B, B vs. C and A vs. C) will be conducted.

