8.2.2 Statistical methods

Analysis of the primary endpoint

The primary analysis will be performed to per-protocol population.

Patients with success is defined by the primary endpoint in Section 7.2.1. The PFSR-OSI-18 in each arm and their 84% confidence intervals will be provided. In case the number of patients analyzed in each arm exceeds or less than what is foreseen above (Section 8.1.1), the 84% confidence interval will be used for the decision.

Time to event endpoints

The analyses of the primary and secondary endpoints will be performed on per-protocol population. Comparison between arms are foreseen for BPFS endpoint only.

Estimates and confidence intervals

Estimates of the median PFS-OSI, TTP-OSI, PFS2-OSI and OS are obtained by the Kaplan Meier technique. The 84% and 95% confidence intervals (CI) for the median will be calculated using the reflected CI method.

Estimates of the event-free rate at fixed time point (18 months) will be obtained using the Kaplan Meier technique and 84% 2-sided CI will be calculated by Greenwood's estimation of the standard deviation. Estimates of hazard ratios and their 84% 2-sided CI will be obtained by Cox regression. In addition 95% 2-sided CI will be provided for both the estimates of event rates and hazard ratios. Kaplan Meier Curves will be drawn for both the experimental and control arms on the same plot.

Inference: Test statistics for comparisons (for BPFS)

Cox regression (Score Test) will be used to compare the experimental versus the control arms adjusted by the stratification factors in randomization (except for centers) at 1-sided 10% significant level.

Toxicity

Analysis for toxicity is based on the safety population. The worst grade of toxicity/adverse events observed over the whole treatment period (excluding re-challenge period for Arm A) according to CTCAE version 4 will be displayed. No formal statistical analysis will be performed to compare toxicity in both arms.

Response Rate

Patients with response categories progression, early death and unknown will be considered as failing to respond to treatment. The response rates in each arm and their 95% confidence intervals will be provided. In addition, response rates in the 2 arms will be compared using a two-sample test at 5% 2-sided level.

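### Brain PFS: 8.1.2, 8.2 and 8.2.2 disagree on the number of comparisons and their level; a Holm rule for A vs B and A vs C settles both and is never less powerful than the fixed 5%/5% split

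*Combined protocol and SAP*

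**What the plan says.** Section 8.1.2 singles BPFS out among the secondary endpoints and names two tests: "Formal comparison between arm A versus B and A versus C with respect to BPFS will be made". The error budget is "With a 1-sided alpha = 5% (so that a 1-sided family wise error: 10%, taking into account 2 comparisons"). The target is "looking for an improvement in BPFS at 18 months from 75% to 87.5"%, described as "equivalent to 54% reduction in risk of progression, i.e. HR = 0.46", and "36 BPFS events will give an approximately 70% power to detect the above difference". No step-down or other sequential rule is mentioned.

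The analysis plan reads differently in two places. Section 8.2 says of BPFS that "comparisons between the arms (i.e. A vs. B, B vs. C and A vs. C) will be conducted", which is three comparisons. Section 8.2.2 says "Comparison between arms are foreseen for BPFS endpoint only" under its time-to-event heading. It then sets the adjusted Cox score test for BPFS at a 1-sided 10% level, without saying whether that is per comparison or for the family. The statistical methods part of the protocol summary repeats the unsplit 10%.

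**The concern.** Two things are at stake.

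- **The error rate is not pinned down.** One section fixes 5% per test and a 10% family; another fixes 10% with no split; a third adds a comparison that the error budget does not count. A p-value of 0.07 for A vs B would be a success under one section and a failure under another.
- **The rule in 8.1.2 is a single-step Bonferroni split.** Each test stays at 5% whatever the other shows. Once the smaller p-value is at or below 5%, Holm's procedure lets the larger be tested at 10% within the same family-wise error. For a comparison planned at only about 70% power, that is power left unused.

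**Working it through.** **Inputs from 8.1.1 and 8.1.2.** 1-sided 5% per test, 10% family-wise, two tests sharing arm A, hazard ratio (HR) 0.46, 36 events, stated power about 70%, 1:1:1 allocation ("using a 1:1:1 ratio for randomization, a total of 156 patients will be accrued in this study (52 pts in each arm"). Check on the HR: ln 0.875 / ln 0.75 = 0.464.

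**Assumptions, not in the documents.** The 36 events are per pairwise comparison. The two test statistics are bivariate normal with correlation 0.5, which is the value for equal information in each arm. Fewer events in arm A would raise it: 12 against 24 events gives (1/12)/(1/12 + 1/24) = 0.67. The range shown is 0 to 0.7.

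**Step 1: reproduce the stated power.** Freedman: power = Φ(√36 × (1 − HR)/(1 + HR) − 1.645).

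- HR 0.46: 6 × 0.54/1.46 = 2.219; Φ(0.574) = 71.7%.
- HR 0.464: 70.9%.

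Both agree with about 70%. Schoenfeld's formula gives 75.3% at HR 0.46, so Freedman is the likelier source. The steps below start from the plan's own 70%, that is, a mean test statistic of 1.645 + 0.524 = 2.169.

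**Step 2: read the 8.2.2 level as 10% per comparison.** Power is Φ(2.169 − 1.282) = 81.3%. Family-wise error when no difference exists:

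| Rule | Correlation 0.5 | Upper bound |
|---|---|---|
| Two tests at 5% | 8.8% | 10% |
| Two tests at 10% | 16.8% | 20% |
| Three tests at 5% | 12.5% | 15% |
| Three tests at 10% | 23.5% | 30% |

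The three-test rows take three equally informative arms. Only the first row respects the 10% in 8.1.2.

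**Step 3: Holm on A vs B and A vs C.** Power for one comparison = P(Z₁ > 1.645) + P(1.282 < Z₁ ≤ 1.645 and Z₂ > 1.645). With HR 0.46 in both and correlation 0.5, this is 70.0% + 6.5% = 76.5%. Over correlations 0 to 0.7 it runs from 77.9% to 75.9%.

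**Step 4: when the two effects differ** (correlation 0.5, power for the comparison with the full effect):

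| Effect in the other comparison (log-HR scale) | 5%/5% rule | Holm |
|---|---|---|
| Full | 70.0% | 76.5% |
| Three quarters | 70.0% | 73.8% |
| Half | 70.0% | 71.7% |
| None | 70.0% | 70.1% |

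In the half-effect row, the weaker comparison itself goes from 28.8% to 39.4%.

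**Step 5: family-wise error of Holm.** With no true difference it equals that of the 5%/5% rule, 8.8% at correlation 0.5. With one true effect at 70% power, the error for the other test is 9.6%, rising towards 10% as the true effect grows. It does not exceed 10% under any dependence.

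**The case against.** The strongest objection is that the fixed 5% tests appear only in the power section. If the 10% in 8.2.2 is the operative level per comparison, power is already about 81%, and Holm would lower it to about 76%. The documents do not say which reading is meant. But the per-comparison reading cannot stand beside the 10% family-wise error in 8.1.2, so it is not a valid benchmark. What stands is that the three sections must be reconciled first, and that adding Holm wording while leaving the 10% sentence in place would make 8.2.2 contradict itself.

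The second objection is B vs C, and it also stands in part. If B vs C is tested at 5% beside the Holm pair, family-wise error with no true difference is about 12.5%. If all three enter one Holm family, the first step is 10%/3 = 3.3%, and Holm no longer always rejects where the 5% rule does. The proposal works only if B vs C is placed outside the formal family, which fits the two comparisons counted in 8.1.2.

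Third, Bonferroni is valid and BPFS is secondary in a phase II trial, so choosing Holm is a matter of efficiency. That is fair, and it limits the weight of the point.

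A reader might also infer three stronger things that the documents do not support:

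- That 76% is an unconditional gain. It needs HR 0.46 in both comparisons. The plan's single effect size makes that a natural planning case, not a guarantee.
- That superiority of A must be shown over both B and C, so that the chance of both tests succeeding (55.7% to 68.7% at correlation 0.5) is the relevant figure. No joint success criterion is stated. If one were, no split would be needed, because each test could be run at 10%.
- That BPFS is the only between-arm test. Section 8.2.2 also plans a two-sample comparison of response rates at a 2-sided 5% level.

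**Conclusion.** The point holds in two linked parts. Sections 8.1.2, 8.2 and 8.2.2 are inconsistent on how many BPFS comparisons are formal and at what level. Taken per comparison, the 8.2.2 level gives about 17% family-wise error for two tests instead of 10% (correlation 0.5; 19% if independent; bound 20%).

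Once the family is fixed as A vs B and A vs C, the single-step split in 8.1.2 is dominated by Holm: same 10% limit, same patients and events, power never lower. The size of the gain rests on the true effects, on the assumed correlation and on 36 events being per pair. It is about 6 to 8 points per comparison when both effects are as planned, and falls to about 2 points or almost nothing otherwise. This is worth doing because it is cheap; it does not touch the primary endpoint.

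**What to change.** Replace the level sentence in 8.2.2, and align 8.1.2, 8.2 and the protocol summary with it:

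> The formal BPFS family is A vs B and A vs C. The smaller 1-sided p-value is tested at 5%; if significant, the larger is tested at 10% (Holm; family-wise error at most 10%). B vs C is descriptive and outside this family.

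In 8.1.2, state whether the 36 events are per comparison. Give the power as about 70% per comparison at minimum when its HR is 0.46, and about 76% if HR 0.46 holds in both, with the correlation assumed.

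**Cost.** A few sentences, agreed before BPFS data are examined. There are two small downsides. When only one effect is real, the error for the other test rises from 5% to at most 10%, still inside the stated budget. Confidence intervals that match a Holm decision are less simple, so the planned 84% and 95% hazard-ratio intervals should be labelled descriptive. Neither level corresponds to a 1-sided 5% test under the present text either.

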8.1.3 Randomization and stratifications

Patients will be centrally randomized (for practical details, see chapter on registration / randomization procedure). A minimization technique will be used for random treatment allocation stratifying by institution, Type of mutation (Del19 vs. L858R), Initial T790M (Yes vs. No) and Brain Metastasis (Yes vs. No).

8.2 Statistical analysis plan

Analyses described below will be done separately for each arm, except for the secondary endpoint BPFS where comparisons between the arms (i.e. A vs. B, B vs. C and A vs. C) will be conducted.

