Cox regression (Score Test) will be used to compare the experimental versus the control arms adjusted by the stratification factors in randomization (except for centers) at 1-sided 10% significant level.

Toxicity

Analysis for toxicity is based on the safety population. The worst grade of toxicity/adverse events observed over the whole treatment period (excluding re-challenge period for Arm A) according to CTCAE version 4 will be displayed. No formal statistical analysis will be performed to compare toxicity in both arms.

Response Rate

Patients with response categories progression, early death and unknown will be considered as failing to respond to treatment. The response rates in each arm and their 95% confidence intervals will be provided. In addition, response rates in the 2 arms will be compared using a two-sample test at 5% 2-sided level.

Translational research

The translational research is mandatory for this protocol. Any patient who consent to enter the trial will have to consent for the translational research.

Objectives

The main objectives of translational research study are, but not limited to, the following:

 to describe quantitatively the presence of T790M EGFR mutations and original activating EGFR mutations in plasma of patients treated with

- gefitinib and osimertinib longitudinally within the arms and to compare the presence of these mutations across the arms A, B and C.
- to describe the associations between the presence of these mutations and response evaluations by RECIST 1.1 longitudinally within the arms.
- to describe the associations between the presence of these mutations and response and PFS to osimertinib in Arm A, B and C.
- to assess mechanisms of resistance to osimertinib in formalin-fixed paraffin-embedded (FFPE) samples obtained from patients at baseline and at the time of progress on osimertinib by next generation sequencing and compare the presence of molecular resistance alterations in tissue samples and plasma samples taken on progression.

Human Biological material

- plasma sample taken during screening visit and each treatment visit (every 4 weeks) while patients are within active treatment with gefitinib or osimertinib. Note: if gefitinib or osimertinib is temporarily discontinued due to toxicity, plasma sample should still be obtained. The last plasma sample should be taken from patients who progress on osimertinib by RECIST 1.1 evaluation (all three arms).

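### Section 8.2 lists three BPFS comparisons against a two-comparison error budget in 8.1.2, and the status of B vs C and the per-comparison test level are left open

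*Combined protocol and SAP*

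**What the plan says.** Section 8.1.2 singles out BPFS among the secondary endpoints and limits formal testing to two pairs: "Formal comparison between arm A versus B and A versus C with respect to BPFS will be made". It sets one-sided alpha at 5% per comparison, "so that a 1-sided family wise error: 10%, taking into account 2 comparisons". The design effect is an 18-month BPFS of 75% against 87.5% (HR 0.46), for which 36 events are said to give approximately 70% power.

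Section 8.2 makes BPFS the exception to separate analysis of each arm: "comparisons between the arms (i.e. A vs. B, B vs. C and A vs. C) will be conducted". The three pairs are listed without distinction.

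Section 8.2.2, under an inference heading restricted to BPFS, says "Cox regression (Score Test) will be used to compare the experimental versus the control arms". The test takes account of the randomization factors apart from centre, and its level is put at one-sided 10%. It does not say whether that 10% is per comparison or for the family. The protocol summary carries the same sentence without the BPFS restriction in its heading. On intervals, 8.2.2 says "Estimates of hazard ratios and their 84% 2-sided CI will be obtained by Cox regression", with 95% intervals in addition.

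**The concern.** A family-wise claim holds only for the set of tests it was computed for. Section 8.1.2 counts two tests and 8.2 names three. The third has no share of the error, no target difference and no power statement. BPFS is the only time-to-event endpoint on which the arms are to be compared, so this is where the trial's comparative inference on such endpoints sits. If B vs C is tested at the same level as the other two, the 10% reported with the results would be wrong.

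The level itself is also unclear. 8.1.2 says 5% per comparison; 8.2.2 and the summary say 10% without a qualifier. An analyst working from 8.2.2 alone could run each test at 10%, and the 10% family-wise limit would then fail even with two tests.

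**Working it through.** **Inputs.** From 8.1.2: two comparisons, one-sided 5% each, 10% family-wise, 75% to 87.5%, HR 0.46, 36 events, about 70% power. From 8.2: three comparisons. From 8.2.2: one-sided 10%; 84% and 95% intervals. From 8.1.1: 1:1:1 allocation; one-sided alpha 0.08 for the single-arm primary design.

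**The plan's own figures.**
- HR = ln 0.875 / ln 0.75 = 0.464, given as 0.46.
- Power by Freedman's formula, Φ(√d·(1−HR)/(1+HR) − z): √36 × 0.54/1.46 = 2.219; 2.219 − 1.645 = 0.574; Φ = 71.7%. With HR 0.464 it is 70.9%. This reproduces the stated figure. Schoenfeld's formula gives 75.3%, so Freedman is the closer match.
- Family-wise bound: 2 × 5% = 10%, as stated.

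**Family-wise error with shared arms.** Under the global null with equal information per arm, take Z_AB = (A−B)/√2, Z_AC = (A−C)/√2 and Z_BC = (B−C)/√2, with A, B and C independent standard normals. Z_AB and Z_AC correlate at 0.5. The two-test values come from the bivariate normal distribution, the three-test values from 8 million simulated draws.

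| Level per test (one-sided) | Two tests: bound / shared arms | Three tests: bound / shared arms |
|---|---|---|
| 5% (8.1.2) | 10% / 8.8% | 15% / 12.6% |
| 10% (8.2.2, if per comparison) | 20% / 16.8% | 30% / 23.5% |
| 3.33% (10% split three ways) | 6.7% / 6.0% | 10% / 8.6% |

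The three-test result at 5% is the same to one decimal whichever direction B vs C is tested. If B vs C is tested two-sided at 5% in total, it is 12.3%.

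**Is B vs C inside the test?** The inference sentence compares experimental with control arms. The treatment section of the summary labels A and B as intervention and C as active control. On those labels B vs C fits the sentence, whereas A vs B, which 8.1.2 does budget, is a comparison of two intervention arms. The sentence therefore neither excludes B vs C nor reproduces the pair of tests in 8.1.2.

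**Power if three tests are kept within 10%.** At 3.33% each, z = 1.834; 2.219 − 1.834 = 0.385; Φ = 65.0% with 36 events. Recovering 70% takes 41 to 42 events (Freedman, HR 0.46 to 0.464).

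**Intervals.** The tail of a two-sided interval is (1 − level)/2. An 84% interval has 8% per tail (z = 1.405), as in the primary design. A one-sided 5% test corresponds to 90% (z = 1.645), a one-sided 10% test to 80% (z = 1.282). Neither planned interval, 84% or 95%, matches either stated BPFS level. With 36 events the boundary hazard ratio is exp(−2z/√36): 0.578 at 5%, 0.626 for the 84% interval, 0.652 at 10%.

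**The case against.** The strongest reply is that 8.1.2 reserves formal comparison for A vs B and A vs C and ties its 10% to those two. For them the claim is true at 5% each. Section 8.2 says only that comparisons will take place and gives B vs C no level, so B vs C may be meant as a descriptive hazard ratio. Likewise, the 10% in 8.2.2 may be the family-wise figure of 8.1.2 repeated. Both readings are possible, and they are why the excess is conditional. The text establishes neither: 8.2 does not separate B vs C from the other pairs, and 8.2.2 attaches its 10% to the test itself.

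A reader might go further in three ways that the documents do not support.

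- That the 10% limit is definitely broken. This needs B vs C to be formally tested, or 10% to apply per comparison, and neither is stated. A larger excess, 16.3%, appears if B vs C is read in either direction at 5% per tail, but that is a two-sided 10% test that the plan nowhere contains.
- That the 84% interval adds type I error or will exclude 1 beside a non-significant test. BPFS is judged by the score test; 8.2.2 makes the 84% interval a decision tool only for the primary endpoint, and 95% intervals are also given. The direction of any discordance depends on the level. At 5%, hazard ratios from 0.578 to 0.626 fail the test while the 84% interval excludes 1. At 10%, those from 0.626 to 0.652 pass while it includes 1.
- That the summary extends the test to other time-to-event endpoints. Sections 8.2 and 8.2.2 both confine such comparisons to BPFS.

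**Conclusion.** The inconsistency stands: two comparisons are budgeted, three are listed, and the test level is given as 5% in one place and an unqualified 10% in others. The size depends on how the gaps are filled. With A vs B and A vs C alone at 5%, the family-wise error is about 8.8% and the stated 10% holds. With B vs C tested at 5% as well, it is about 12.6%, some 2.6 points over. If 10% is per comparison, it is about 16.8% for two tests and 23.5% for three, so the level matters more than the number of tests. These figures assume the global null, approximately normal score statistics and equal information per arm; the Bonferroni bounds need no assumption about the correlation between the tests. The 84% interval is a reporting mismatch only. The primary endpoint is unaffected, since it is assessed within each arm.

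**What to change.** 1. In 8.2, name A vs B and A vs C as the only formal BPFS tests. Report B vs C as a hazard ratio with confidence interval and no test.
2. In 8.2.2 and the summary, state one-sided 5% per comparison (10% family-wise), as in 8.1.2, and name the two pairs and the direction of each in place of the experimental and control labels. Step 1 alone is not enough: an unqualified 10% would still allow about 16.8%.
3. As minor alignment, give the two tested hazard ratios 90% two-sided intervals in addition to 95%, and carry the BPFS restriction into the summary's inference heading.

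Power stays at about 71% with 36 events. The cost is a few wording changes and no p-value for B vs C, a comparison for which no power was planned. If a formal B vs C test is wanted, the 10% can be split three ways at 3.33% each, with 93.3% two-sided intervals to match. Power then falls to about 65% with 36 events.
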